The second part of the study is an expansion at the MTD. Subjects will be randomized 1:1 to an experimental arm (curcumin) and a control arm (standard of care), with 23 subjects enrolled to each arm. Subjects on the experimental arm will use a mouth rinse containing the MTD of curcumin 3 times each day for 14 days. Subjects on the control arm will use a standard mouth rinse 3 times each day for 14 days. Both mouth rinses will be used for 30 seconds and then swallowed. Subjects will be evaluated for response and toxicity. Statistical analysis of the response data will determine whether oral exposure to curcumin reduces mucositis.

Section	Contents	Page
1	1. BACKGROUND AND SIGNIFICANCE	4
2	OBJECTIVES / ENDPOINTS	5
3	STUDY DESIGN	5
4	SUBJECT SELECTION	6
4.1	INCLUSION CRITERIA	6
4.2	EXCLUSION CRITERIA	6
5	STUDY PROCEDURES AND SCHEDULE	6
5.1	STUDY VISITS	7
5.2	STUDY CALENDAR	10
5.3	PREPARATION OF STANDARD MOUTH RINSE	11
5.4	PREPARATION OF STUDY MOUTH RINSE (CURCUMIN)	11
5.5	STUDY DRUG (CURCUMIN) DOSE	11
5.6	DETERMINATION OF MTD	11
6	EXPECTED ADVERSE EVENTS	12
6.1	DOSE-LIMITING TOXICITY	12
6.2	CRITERIA FOR SUBJECT REMOVAL	12
6.3	CRITERIA FOR STUDY DISCONTINUATION	13
6.4	CRITERIA FOR DOSE REDUCTION	13
6.5	SERIOUS ADVERSE EVENTS (SAEs)	13
7	BENEFITS	13
8	SAMPLE SIZE	13
9	MEASUREMENT OF EFFECT	14
9.1	DETERMINATION OF OBJECTIVE MEASUREMENT OF ORAL MUCOSITIS	14
9.2	DETERMINATION OF SUBJECTIVE MEASUREMENT OF ORAL MUCOSITIS	14
9.3	DETERMINATION OF PAIN ASSOCIATED WITH ORAL MUCOSITIS	14
9.4	DETERMINATION OF DURATION OF MUCOSITIS	15
9.5	DETERMINATION OF TOXICITY PROFILE	15
9.6	CRITERIA TO BE EVALUABLE FOR EFFICACY AND SAFETY	15
10	CORRELATIVE STUDIES (LABORATORY STUDIES)	15
10.1	SAMPLE COLLECTION	15
10.2	EVALUATION OF PROINFLAMMATORY CYTOKINES	15
10.3	FUTURE RESEARCH AND SAMPLE DISPOSITION	16
11	DATA COLLECTION	16
12	MONITORING PLAN	16
13	REPORTING REQUIREMENTS	17
13.1	REPORTING REQUIREMENT FOR SERIOUS ADVERSE EVENTS (SAEs)	18
14	REGULATORY REQUIREMENTS	18
14.1	INFORMED CONSENT	18
14.2	INSTITUTIONAL REVIEW BOARD	19
14.3	SUBJECT CONFIDENTIALITY	19
15	EXPERIENCE OF THE INVESTIGATORS	20
16	REFERENCES	21

APPENDICES: A: DAILY LOG
B: HEALTH CARE PROVIDER ASSESSMENT TOOL
C: SUBJECT ASSESSMENT TOOL
D: BIOSKETCH FOR DR. [name]

1. Background and Significance

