2. Objectives/Endpoints

The primary objective of this Phase I/II study is to determine the maximum tolerated dose (MTD) of oral curcumin in patients who have chemotherapy-induced mucositis. The secondary objectives of this study are to determine whether oral curcumin:

- Decreases an objective measurement of oral mucositis
- Decreases the pain associated with oral mucositis
- Decreases the duration of mucositis
- Has an acceptable safety profile.

3. Study Design

This is a phase I/II study involving 2 parts: a dose escalation part and an expansion at the maximum tolerated dose.

In the first part, there will be 3 subjects at each dose level of curcumin (see table below). The doses will be taken 3 times each day for 14 days. Each dose will be taken as a mouth rinse containing curcumin and water, 3 times each day for 14 days. The mouth rinse will be used for 30 seconds and then swallowed. Subjects will be evaluated for dose-limiting toxicity (DLT, defined in section 6.1). The maximum tolerated dose (MTD, defined in section 2) will be determined. Subjects may participate in the study at a higher dose level, after they have completed the study at the current dose level and if they are eligible.

# Subjects	Curcumin/dose (gram)	Curcumin/day (gram)
3	0.33	1
3	1.0	3
3	2.0	6
3	3.0	9

In the second part of the study, there will be 23 subjects enrolled to an experimental (curcumin) arm and 23 subjects enrolled to a control (standard of care) arm. Subjects will be randomized to take a mouth rinse with or without the MTD of curcumin, 3 times each day for 14 days. The rinses will be swallowed. Subjects will be evaluated for response and toxicity. Subjects in the first part of the study may participate in the second part of the study, if they are eligible.

In both parts of the study, if the mucositis score \leq Grade 2 but is unresolved after 14 days of taking the study mouth rinse (curcumin or control), then the subject will

continue to receive the study mouth rinse until the mucositis is resolved (Grade 0).

This study will involve 12 subjects in the first part, plus an additional 3 subjects if a dose-limiting toxicity occurs (see section 2) and 46 subjects in the second part for a total of 61 subjects. This study is expected to take 2 years to complete enrollment, treatment and follow-up (6 months for the first part and 18 months for the second part).

4. Subject Selection

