5.6 Determination of MTD

The MTD will be determined as follows: If a DLT occurs in any one of the 3 patients at a specific dose level, an additional 3 patients must be treated at that dose level to achieve statistical validity of the MTD. If 2 of the 6 patients (17%) at a dose level develop a DLT, the previous dose level will be used as the MTD. If no DLT is observed, then the MTD will be the highest dose. To ensure safety of subjects at each dose level, all assessments will be completed at Visit 5 for subjects at a dose level before another subject is given study drug at the

subsequent dose level.

6. Expected Adverse Events

Toxicities will be graded by health care providers using the Common Terminology Criteria for Adverse Events (CTCAE) Version 4.0 weekly after initiation of study mouth rinse until mucositis is resolved (Grade 0) (see Provider Assessment in calendar, section 5.2). Toxicities will be assessed by subject self-evaluation during study mouth rinse administration between clinic visits (see Subject Assessment in calendar, section 5.2).

Very few studies have reported any severe or serious side effects from curcumin and most studies have involved oral administration of curcumin. No major toxicity has been found in studies where curcumin is used short-term. Increased bleeding may occur due to inhibition of platelet aggregation (very rare). Possible other side effects associated with curcumin include: vomiting, nausea, rash and GI distress. In a study of subjects with colon cancer, oral curcumin at doses ranging from 0.45 to 3.6 gram/day for 1 to 4 months was associated with nausea and diarrhea and caused an increase in serum alkaline phosphatase and lactate dehydrogenase[15]. In one study of patients with advanced pancreatic cancer, 5 of the 17 patients receiving oral curcumin (8 gram/day) in combination with gemcitabine reported intractable abdominal pain after a few days to 2 weeks of curcumin intake[16]. In a recent study of topical curcumin for mucositis in juveniles and children[14], there were no oral adverse events documented and no systemic adverse events that possibly could be related to the use of the curcumin mouthwash.

Patients will receive full supportive care as appropriate. The rationale for treatment, dosage and the date of treatment will be recorded in the medical record.

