This study will involve 12 subjects in the first part, plus an additional 3 subjects if a dose-limiting toxicity occurs (see section 2). This sample size is similar to other phase I dose escalation studies and will result in a determination of maximum-tolerated dose. The first objective for the second part (n=46) is to determine whether curcumin decreases an objective measurement of oral mucositis. Mucositis assessment will be conducted by the provider using the WHO scale and CTCAE scale. The scales are continuous between 0 and 4. Analysis of variance will be used to compare the two groups of subjects (standard mouth rinse versus study mouth rinse) separately for each time period (baseline and each week after study mouth rinse initiation). In a one-way ANOVA study, sample sizes of 23, and 23 are obtained from the 2 groups whose means are to be compared. The total sample of 46 subjects achieves 91% power to detect differences among the means versus the alternative of equal means using an F test with a 0.05 significance level. The size of the variation in the means is represented by their standard deviation which is 0.50. The common standard deviation within a group is assumed to be 1.00.

9. Measurement of Effect

Differences between the two mouth rinse groups will be studied with the chi-square test for categorical factors and the analysis of variance F-test for continuous variables with a 0.05 significance level.

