9.5 Determination of toxicity profile

Toxicities will be graded by health care providers using the Common Terminology Criteria for Adverse Events (CTCAE) Version 4.0. A baseline evaluation will occur prior to study mouth rinse administration, and then weekly during study mouth rinse administration. Data will be recorded and entered into a database.

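### The Part 2 safety objective has no planned analysis beyond a general test for a difference at 0.05, and with 23 per arm that test cannot support a conclusion of acceptable safety

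*Combined protocol and SAP*

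**What the plan says.** Section 2 lists four secondary objectives. The last is to determine whether oral curcumin "Has an acceptable safety profile". No toxicity rate, margin or confidence bound defines acceptable.

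Section 3 says that Part 2 subjects are evaluated for both response and toxicity. Section 9 opens with one general rule for comparing the arms: "Differences between the two mouth rinse groups will be studied with the chi-square test for categorical factors". Continuous measures are to be compared by an ANOVA F test, also at the 0.05 level. Under that section, 9.5 deals with toxicity: "Toxicities will be graded by health care providers using the Common Terminology Criteria for Adverse Events (CTCAE) Version 4.0", at baseline and weekly, with the data entered into a database. It names no summary measure, test or criterion. Section 9.6 says who is evaluable for safety (at least one dose taken), not how safety is judged.

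Section 8 sizes Part 2 on the mucositis score alone: "The total sample of 46 subjects achieves 91% power to detect differences among the means". No power or precision is given for toxicity.

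The plan has other safety rules: the DLT definition (6.1), the MTD rule (5.6), removal of a subject with a DLT (6.2), closure after two DLTs at dose 1 and a hold for any Grade V toxicity (6.3), dose reduction (6.4), and review by the investigator, the IRB and an independent monitor (Section 12).

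**The concern.** The chi-square and F tests take equal toxicity as the null hypothesis. They can show that the arms differ. They cannot show that curcumin toxicity is low enough, which is what the objective asks. If the arms do not differ significantly, the plan gives the analyst no other quantity to report and nothing to prevent that result from being presented as support for the objective.

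This matters because the dose taken into Part 2 may rest on as few as 3 to 6 Part 1 subjects. Part 2 therefore supplies most of the safety evidence at that dose. With 23 per arm, a moderate excess of toxicity is quite likely to be non-significant.

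**Working it through.** **Inputs.** From the documents: 23 subjects per arm (Sections 3 and 8), tests at 0.05 (Section 9), within-group SD 1.00 and SD of the two means 0.50 (Section 8). Assumed: all Part 2 toxicity rates, because the plan gives none; a chi-square without continuity correction, because the plan names none; and all 23 subjects per arm evaluable.

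**1. The plan's own power figure.** For two equal groups, an SD of means of 0.50 is a difference of 1.0, so f = 0.50/1.00 = 0.5. The non-centrality is 46 × 0.5² = 11.5 on 1 and 44 df. Power is 0.912, which reproduces the stated 91%. It applies to the mucositis score only.

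**2. Chance of missing a true excess.** For x events on control and y on curcumin, with n = 23 and N = 46,

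X² = N[y(n − x) − x(n − y)]² / [n²(x + y)(N − x − y)],

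significant if X² > 3.84. Summing binomial probabilities over all 24 × 24 tables, and counting as detected only those significant with more events on curcumin, gives:

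| Control rate | Curcumin rate | Missed |
|---|---|---|
| 10% | 20% | 84% |
| 10% | 25% | 73% |
| 10% | 30% | 59% |
| 10% | 40% | 31% |
| 10% | 50% | 12% |
| 5% | 25% | 49% |
| 20% | 60% | 18% |

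The uncorrected test is the favourable choice. Fisher's exact test has power of 18% at 10% vs 25% and 30% at 10% vs 30%, so it misses 82% and 70%.

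Section 6 does cite one rate in adults: 5 of 17 (29%) with intractable abdominal pain on 8 g/day of curcumin with gemcitabine. A true 29% would be missed 60% of the time against an assumed 10% control rate, and 35% against 5%.

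**3. What a non-significant result can look like.** Take 7/23 on curcumin (30.4%) and 2/23 on control (8.7%):

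X² = 46 × (7 × 21 − 2 × 16)² / (23² × 9 × 37) = 46 × 115² / 176,157 = 3.45, p = 0.06.

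The difference is 21.7 points. The Wilson limits are 15.6% to 50.9% and 2.4% to 26.8%. The Newcombe 95% interval for the difference is:

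- lower: 21.7 − √[(30.4 − 15.6)² + (26.8 − 8.7)²] = about −2 points
- upper: 21.7 + √[(50.9 − 30.4)² + (8.7 − 2.4)²] = about +43 points

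A result reported only as non-significant would hide an interval reaching +43 points.

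**4. Continuous safety values.** For a shift of 0.5 SD in a CMP or INR value, f = 0.25 and the non-centrality is 46 × 0.0625 = 2.875. The F test misses it 62% of the time.

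**5. What estimation would give.** The exact one-sided 95% upper bound for the curcumin arm is 1 − 0.05^(1/23) = 12.2% after 0/23, and 30.4% after 3/23 (95th percentile of a Beta(4, 20) distribution).

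**The case against.** The strongest reply is that the link from the safety objective to a p-value is inferred. The opening sentence of Section 9 does not mention toxicity, the section is about measurement of effect, and 9.5 is compatible with purely descriptive reporting of grades. No passage says that a non-significant test will be read as acceptable. That stands. A reader might infer that the plan equates p > 0.05 with acceptable safety, but the documents do not say so. What remains is that 9.5 falls under the Section 9 rule and offers nothing in its place. If that rule were held not to cover toxicity, the objective would have no analysis at all.

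A second reply is that safety is also protected by the DLT and MTD rules, closure at dose 1, the Grade V hold, subject removal and ongoing review. These are real safeguards and serve their own purposes. None says how Part 2 toxicity is to be judged at the end. The escalation data are also too few to settle it: the one-sided 95% upper bound on the DLT rate is 63% after 0/3 and 58% after 1/6.

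A third reply is that a 46-subject early-phase trial need not be powered for safety. That is correct. Low power is a limitation rather than an error, and Section 8 claims no safety power. It is, however, the reason to estimate rather than test.

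**Conclusion.** The point holds as a gap in the analysis plan. The safety objective has no Part 2 analysis beyond a general test for a difference, and at 23 per arm that test cannot support a conclusion of acceptable safety.

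From an assumed 10% control rate, a 15- to 20-point excess is missed about 59% to 73% of the time. These figures rest on assumed rates and the uncorrected chi-square. They vary with the control rate: a 20-point excess from 5% is missed 49% of the time.

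A reader might go further and conclude that almost any excess would be missed unless the control rate were near zero. The calculations do not support that: 10% vs 50% is missed 12% of the time and 20% vs 60% is missed 18%. The weakness concerns moderate excesses. It should be corrected, but it does not undermine the design.

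**What to change.** In Sections 9 and 9.5, state that Part 2 safety will be assessed by estimation:

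- Report, for each arm, the proportion with a DLT and the proportion with any grade 3 or greater toxicity, with exact confidence limits.
- Report the between-arm risk difference with a 95% confidence interval, and the mean difference with a 95% interval for CMP and INR values.
- State that p > 0.05 will not be read as evidence of acceptable or similar safety.

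A mandatory pass/fail limit on the curcumin arm alone is not proposed. These are chemotherapy patients, and any grade 3 or greater toxicity would count, so background toxicity could decide the result. For example, a rule allowing at most 3/23 would be met only 54% of the time at a true rate of 15%. The randomized comparison should carry the interpretation.

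Separately, Section 5.6 reads "If 2 of the 6 patients (17%) at a dose level develop a DLT, the previous dose level will be used as the MTD". Two of six is 33%; 17% is one of six. The count and the percentage need to be reconciled.

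The cost is a few sentences, with no new data, visits or patients. The intervals will be wide, so some results will have to be reported as inconclusive.

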9.1 Determination of objective measurement of oral mucositis

The objective measurements of oral mucositis will be obtained by a health provider's assessment of mucositis. Providers will be uninvolved, trained oncology clinic staff (not affiliated with the study) to reduce bias. Providers will use the Common Terminology Criteria for Adverse Events (CTCAE) Version 4.0 and World Health Organization's (WHO's) Oral Toxicity Scale (OTS). They will be instructed to circle where on the scale they would assess the subject's mucositis level. A baseline evaluation will occur prior to study mouth rinse administration, and then each week after study mouth rinse initiation. The Health Care Provider Assessment Tool is attached as Appendix B.

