4.2 Exclusion Criteria

- Current use of therapeutic doses of anticoagulants such as warfarin or antiplatelet agents (prophylactic doses and agents are acceptable)
- Biliary tract obstruction or cholelithiasis
- History of gastric or duodenal ulcers or hyperacidity syndromes
- AST or ALT $>$ 2 x ULN
- Total bilirubin \geq 2 x ULN
- INR $>$ 1.5
- Previous stem cell transplant (allogeneic or autologous)
- Preexisting oral disease, such as active oral infection, trauma to the oral mucosa or oral ulceration prior to chemotherapy
- Known allergy/hypersensitivity to curcumin, yellow food colorings, or other members of the Zingiberaceae (ginger) family
- Pregnant or breastfeeding

Potential subjects are identified by medical record review. Eligible subjects are asked to give their written consent to participate in this study. The tests required to screen subjects for this study include a pregnancy test, INR and CMP.

5. Study Procedures and Schedule

The study mouth rinse will be initiated when subjects have $>$ grade 2 mucositis, which could be at any point during their chemotherapy cycle. Subjects who develop $>$ grade 2 mucositis will receive appropriate adjustments in their chemotherapy dose to reduce toxicity with subsequent cycles.

In the first part, there will be 3 subjects at each dose level of curcumin. Each dose will be given as a mouth rinse containing curcumin and water.

In the second part, subjects will be randomized to take a mouth rinse with the MTD of curcumin or a standard mouth rinse, 3 times each day for 14 days. The curcumin mouth rinse will be designated “study mouth rinse” to differentiate it from the standard mouth rinse.

All subjects will be instructed to rinse their mouths with the study or standard mouth rinse 3 times each day for 14 days. Subjects will be instructed to use the study or standard mouth rinse for 30 seconds and then swallow the rinse. Subjects will be instructed not to eat within one hour after using the study or standard mouth rinse. Subjects will be instructed to use a saline mouth rinse after eating any food to keep their mouth clean. A daily log (Appendix A) will be available for each subject and will include a checklist that will simplify the rinsing schedule as well as an area for the subject (or family member) to document mouth rinse administration. No other adjunctive topical treatment will be used during the study.

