This visit will occur 7 days (+/- 1 day) after Visit 2. A mucositis assessment (CTAE version 4.0 and WHO Oral Toxicity Scale) will be conducted and documented by a health provider (Appendix B), who will also review and follow up on any side-effects that the subject is experiencing and check the daily log (Appendix A) to ensure that the subject is complying with the study. Sufficient mouth rinse will be given to the subject for the second week of the study. A blood sample will be obtained to assess liver function (CMP) and clotting function (PT and INR). A blood and saliva sample will be obtained for research purposes (section 10). This visit will take approximately 30 minutes.

5.1.5 Phone call 2

On day 10 or 11 after the first day of taking the mouth rinse for the study, the subject will be called by a study staff member, who will review and follow up on any side-effects that the subject is experiencing and answer any questions about the study or study mouth rinse. The staff member will remind the subject to complete a subject self-assessment tool (Appendix C) and the daily log (Appendix A) and bring them to the next visit. The phone call will take about 15 minutes.

5.1.6 Visit 4

This visit will occur 7 days (+/- 1 day) after Visit 3. A mucositis assessment (CTAE version 4.0 and WHO Oral Toxicity Scale) will be conducted and documented by a health provider (Appendix B), who will review and follow up on any side-effects that the subject is experiencing and obtain the daily log (Appendix A) from the subject. A blood sample will be obtained to assess liver function (CMP) and clotting function (PT and INR). A blood and saliva sample will be obtained for research purposes (section 10). If the mucositis score \leq Grade 2 but is unresolved, then the subject will continue to receive the study mouth rinse (curcumin or standard mouth rinse) until the mucositis is resolved (Grade 0). Sufficient mouth rinse will be given to the subject for the subsequent week of the study. This visit will take approximately 30 minutes.

5.1.7 Phone call 3

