5.2 Study Calendar

Study Procedure	Visit 1 (Screening)	Week 1		Week 2		Week 3		Week 4- mucositis resolution		Final visit
	day -1	Visit 2: day 0	Phone call 1: day 3	Visit 3: day 7	Phone call 2: day 10	Visit 4: day 14	Phone call 3: day 17	Visit: For phase II: weekly cycle repeated until mucositis is resolved (and no AEs)	Phone calls	
activity window		At or w/in 48hr of Visit 1	+ 1 day	+/- 1 day	+ 1 day	+/- 1 day	+ 1 day	+/- 1 day	+ 1 day	+/- 1 day
Sign Informed Consent	X									
Oral exam for hygiene	X									
Pregnancy test	X ¹									
Provider mucositis assessment ²	X	X ³		X		X		X ^a		X
Provider supplies study mouth rinse		X		X		X ^a		X ^a		X
Provider supplies study journal, self-assessment		X		X		X ^a		X ^a		X
Provider collects journal and self-assessments				X		X		X ^a		X
Remind subject to complete self-assessment		X	X		X		X		X ^a	
Blood collection for liver function (CMP) ⁴	X			X		X		X ^a		X
Blood collection for clotting (PT and INR) ⁴	X			X		X		X ^a		X
Research blood collection ⁵		X		X		X		X ^a		
Research saliva collection ⁵		X		X		X		X ^a		
Collect AEs			X	X	X	X	X	X ^a	X ^a	X
Review of concomitant medications	X	X		X		X		X ^a		X

¹ Blood or urine pregnancy test, if not already done as part of standard of care

² Includes CTAE version 4.0 and WHO oral Toxicity scale.

³ Mucositis assessment at Visit 2, only if a different day than Visit 1 (does not need to be repeated if Visit 1 and 2 are done on the same day)

⁴ Does not need to be repeated if already done for standard of care.

⁵ 6 ml of peripheral blood into a non-anti-coagulated tube, 2 ml saliva into a sterile tube; processed and stored as described in the operations manual.

^a Only if subject is still taking study mouth rinse based on improvement of mucositis at each visit, beginning at visit 4.

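### The uninvolved mucositis graders of section 9.1 are given log, side-effect and (by the calendar) dispensing tasks elsewhere, so in Part 2 nothing shields the grader from learning the arm

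*Combined protocol and SAP*

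**What the plan says.** Section 9.1 gives the grading of mucositis (CTCAE and WHO scales, form in Appendix B) to clinic staff outside the study and states the purpose: "Providers will be uninvolved, trained oncology clinic staff (not affiliated with the study) to reduce bias".

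The visit sections give that same provider further tasks:

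- **Visit 3 (5.1.4):** the health provider who documents the mucositis grade is the person "who will also review and follow up on any side-effects that the subject is experiencing and check the daily log (Appendix A) to ensure" compliance.
- **Visit 4 (5.1.6), Visit 5 (5.1.8) and later weekly visits (5.1.10):** the grading provider is the person "who will review and follow up on any side-effects that the subject is experiencing and obtain the daily log (Appendix A) from the subject". At Visit 5 the log is obtained only if the rinse is still in use.
- **Calendar (5.2):** besides the row for the provider's mucositis assessment there are rows reading "Provider supplies study mouth rinse" and "Provider collects journal and self-assessments".

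Section 5 describes the daily log as a rinsing checklist with "an area for the subject (or family member) to document mouth rinse administration".

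The Part 2 rinses do not resemble each other. Section 5.3 describes a pharmacy-prepared Benadryl, Maalox and lidocaine liquid in 200 mL bottles. Section 5.4 describes curcumin powder in vials that the subject mixes with sterile water at home. The protocol contains no provision that masks subjects or graders, or that withholds the arm from the grader.

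**The concern.** With openly different rinses and no masking, the independence of the grader is the only stated protection for the provider-graded outcome. A person who checks rinse compliance, follows up side-effects of the rinse and perhaps hands it out is doing study work. That person also has several occasions to learn which rinse the subject uses.

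The grade has wide reach in Part 2:

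- It is the measure on which the 46 subjects are sized (section 8).
- It determines healing time, counted in days to grade 0 (section 9.4).
- It enters the lack-of-activity rule, which stops the study if fewer than 5 of the first 10 curcumin subjects are at Grade 0 at Visit 4 (section 6.3).

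For the first two, expectations about an arm can create or hide a difference. The third counts curcumin subjects only. There, lenient or strict grading would move the count, and so the decision to continue, rather than a comparison between arms.

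**Working it through.** **1. Do the sections describe one person or two?** In 5.1.4, 5.1.6, 5.1.8 and 5.1.10 a single sentence names the health provider who grades, then attaches the side-effect and log tasks to that provider with the word *who*. For the telephone calls (5.1.3, 5.1.5, 5.1.7, 5.1.9) the protocol uses a different term, a study staff member. So the visit text, read as written, gives all these tasks to the grader. The calendar's *Provider* may be a generic label. The conflict with 9.1 does not depend on it.

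**2. Reproduce the plan's figure.** Inputs from section 8: 23 per arm, F test at 0.05, standard deviation of the means 0.50, within-group SD 1.00. For two means, a standard deviation of 0.50 (divisor 2) corresponds to a difference of 2 × 0.50 = 1.0 grade.

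- Noncentrality: λ = (n/2) × (difference/SD)² = (23/2) × (1.0/1.0)² = 11.5
- Power of the F test with 1 and 44 degrees of freedom: 0.912

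This agrees with the stated 91%, so the same model can be used for sensitivity.

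**3. Effect of a grading shift when there is no true effect.** The documents give no value for assessor bias, so the shift b (average difference in grading between arms, in grades) is assumed. Then λ = 11.5 × b², and the rejection probability comes from the same noncentral F distribution. The last column translates b into the number of subjects in one arm of 23 who would have to be graded one full grade off (23 × b).

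| Assumed b | λ | Chance of p < 0.05 | 23 × b |
|---|---|---|---|
| 0 | 0 | 0.050 | 0 |
| 0.1 | 0.115 | 0.063 | 2.3 |
| 0.25 | 0.719 | 0.132 | 5.8 |
| 0.5 | 2.875 | 0.382 | 11.5 |

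For scale, the smallest significant difference at an observed SD of 1.0 is 2.015 × √(2/23) = 0.59 grade.

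**4. Effect of a shift against curcumin when the true difference is 1.0 grade.** The expected difference becomes 1.0 − b. Power falls from 0.912 to 0.847 (b = 0.1), 0.701 (b = 0.25) and 0.382 (b = 0.5).

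These figures are for a single comparison at one time point. Section 8 plans a separate analysis at baseline and at each week.

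**The case against.** The strongest reply is that *uninvolved* and *not affiliated* describe where the assessor works, and that the protocol never promises blinding. On this view unaffiliated clinic staff may ask about side-effects without breaking 9.1. This stands in part. The side-effect task is the weaker conflict, and checking the log for study compliance is the firmer one. It also means that a reader who infers a broken promise of masked assessment goes further than the text. What is defeated is the stated aim of reducing bias through an uninvolved assessor.

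A reader might also infer that the grader knows the arm. No section says so. Appendix A was not available for this review, so whether the log names the rinse could not be checked. Both arms use 15 mL three times a day, so a completed log need not reveal the arm. The term *study mouth rinse* does not settle it either: section 5 reserves it for curcumin, while the visit sections use it for both arms. The supportable statement is that the grader is not shielded from learning the arm.

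The sizes are open to challenge too. The shifts are hypothetical, 0.5 grade is half of the whole design difference, and at 0.1 grade the inflation is slight. In addition, the MTD is the primary objective and mucositis reduction is secondary (section 2). All of this limits how serious the point is. It does not remove the contradiction, which bears on the measure used to size Part 2.

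**Conclusion.** The point holds as an internal contradiction with a bearing on bias. Section 9.1 relies on uninvolved graders, the visit sections give those graders study tasks, and no provision keeps the arm from them in Part 2. The documents do not show that graders know the arm, nor that grading will be biased.

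The possible size runs from negligible to serious: a false-positive rate of about 6%, 13% or 38% in place of 5% for an assumed shift of 0.1, 0.25 or 0.5 grade. This rests on section 8's own model (23 per arm, SD 1.0, scale treated as continuous) and on shifts that are assumptions. Part 1 has no comparison between arms, so the concern is confined to Part 2. It should be corrected before Part 2 starts, and the sample size need not change.

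**What to change.** For Part 2, reconcile section 9.1 with sections 5.1.4 to 5.1.10 and 5.2:

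- The uninvolved clinic provider completes Appendix B first at each visit. This provider is not told the arm and does not see the daily log, self-assessments, rinse supply or side-effect notes.
- Existing study staff then check the log, collect journals and self-assessments and hand out the rinse. The *Provider* labels in the calendar are changed to match. Sections 9.2 and 9.3, where providers fill in the self-assessment form, should say that this is not the grader.
- Side-effect follow-up and CTCAE toxicity grading come after the mucositis grade is recorded and remain with a health care provider, as sections 6 and 9.5 require. This is preferably someone other than the grader, because what is learned at one visit carries over to the next.
- Section 9.1 states that Part 2 graders are kept unaware of the arm.

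The cost is slightly more coordination at each visit. The title page lists study coordinators, and study staff already review side-effects by telephone, but the protocol does not describe their availability at visits, so the sponsor should confirm it. A second health care provider for toxicity grading would add some effort. Masking will be imperfect if subjects mention their rinse, so they should be asked not to discuss it with the grader.
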